Socially Assistive Robots for Interaction With Older Adults With Dementia

NCT04384978

Date: 4/20/2021

Objectives.

The study will evaluate the overall effectiveness of Ryan Companionbot (aka Ryan) with interactive gameplay to have a positive impact on a user's cognitive function, performance of activities of daily living, and mood. An active control group will perform solitary physical and cognitive activities such as walking and crossword puzzles, sudoku, or solitaire. Our hypothesis is individuals playing interactive cognitive and physical games with Ryan will have a greater positive effect on cognitive function, performance of activities of daily living, and mood compared to individuals engaging in solitary physical and cognitive activities.

Design.

The study addresses design and analysis problems common to published brain training intervention studies and follows recommended best practices of preregistration, adequate documentation, pretest baseline, control conditions, sampling and randomization, dosing, blinding, contingent analysis, statistical analysis, and scattershot publishing without full documentation. The pilot study will be comprised of two groups of people diagnosed with mild Alzheimer's disease and related dementia senior subjects. Subjects will play games with and administered by Ryan, 2-3 times a week and 30-minutes per day. The team will measure the changes and improvement in the social/emotional well-being of these two groups and eventual changes in the cognitive/memory functions of elderly people living in a similar environment.

Methods.

The study with Ryan CompanionBot will occur in ESC's and Kavod's library or atrium or a location free of distractions and intrusion. A staff member will be present during all sessions to assist with user operation, document behavioral observations, and ensure the safety of participants by intervening if the subject shows signs of distress. Ryan's sensors will record all of the subject's activities and interactions including the gameplay. The system will record all dialogs between the subjects and Ryan, along with Ryan's decisions for additional analysis of the individuals' behaviors. Prior to running the sessions, we will interview each participant and his/her caregivers to understand the main weaknesses and problems related to physical and cognitive limitations from their dementia, and to learn about their favorite colors, objects, animals, music, names of close relatives, and cherished belongings to personalize the experience. Participants will complete the Saint Louis University Mental Status (SLUMS) test, a screening method for Alzheimer's and other dementia. Scores range from 0 to 30. Scores of 27 to 30 are considered normal in a person with a high school education. Scores between 21 and 26 suggest a mild neurocognitive disorder. Scores between 0 and 20 indicate dementia. The measurement will be conducted three times throughout the study.

Statistical Analysis Plan.

Statistical analysis will include multi-way Analysis of Variance (ANOVA) to find the significance of the findings and the effect of different parameters and variables on the measured outcomes within and between the two groups.

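### Objectives hypothesise superiority on cognition, daily living and mood, but this document states no daily-living measure and no defined mood measure

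*Combined protocol and SAP*

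**What the plan says.** Objectives give a broad aim: "The study will evaluate the overall effectiveness of Ryan Companionbot". The comparator is solitary activity ("An active control group will perform solitary physical and cognitive activities"), and the hypothesis is directional and covers three effects: the Ryan group "will have a greater positive effect on cognitive function, performance of activities of daily living, and mood compared to individuals engaging in solitary" pursuits.

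Design calls the study a pilot and states two intentions to measure. One is near to mood: "The team will measure the changes and improvement in the social/emotional well-being of these two groups". The other is cognition: "eventual changes in the cognitive/memory functions of elderly people living in a similar environment". Neither comes with an instrument. Design also says that the study "follows recommended best practices of preregistration, adequate documentation, pretest baseline", and the same list goes on to "control conditions, sampling and randomization".

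Methods name one instrument, SLUMS, scored 0 to 30 and described as a screening method. It is given three times, with no week, visit or interval. Methods also mention an interview before the sessions, staff observations, and recordings by Ryan's sensors.

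The SAP is one sentence. It plans a multi-way ANOVA of whatever outcomes are measured, both inside each group and across the two. It names no dependent variable.

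**The concern.** A hypothesis about an effect needs a measure of that effect, taken in both groups at known times. Here the hypothesis has three parts and the rest of the document equips one of them. If no ADL scale is given during the study, no later analysis can supply the missing data. If the mood scale and its time point are settled late, they may be settled by someone who has seen results. A report could then claim overall effectiveness when only cognition had been measured by an instrument fixed in advance.

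**Working it through.** No sample size, power or effect size is given, so there is no figure of the plan's own to reproduce. The check sets the sections side by side.

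| Effect in Objectives | Design | Methods | SAP |
|---|---|---|---|
| Cognitive function | Intention to measure | SLUMS, 0 to 30, three times, undated | Not named |
| ADL | Nothing | No scale | Not named |
| Mood | Intention to measure social and emotional well-being | No scale | Not named |

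Count: 3 hypothesised effects, 1 with a named instrument, 2 without. SLUMS assessments: 3, of which 0 are dated.

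**ADL.** Daily living is named twice, both times in Objectives. Three data sources in Methods might be thought to stand in for a measure:

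- The interview asks about physical and cognitive limitations. It is held before the sessions, with no score and no stated repeat, so it gives no outcome.
- Ryan's sensors record what the participant does with Ryan, in a library, atrium or similar place. No text derives an ADL score from the recordings or places the sensors in control sessions.
- Staff observations have no stated scoring or link to ADL, and the text does not say whether control sessions are covered.

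None is offered by the document as an ADL measure.

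**Mood.** Design commits to measuring well-being in both groups. Treating that as the mood outcome, the instrument, the score and the time points are all still missing.

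**Cognition.** SLUMS has a name and a score range. Its role as an outcome is inferred from its being repeated, since the text calls it only a screening method. Design's pretest baseline suggests that one assessment comes before treatment, but no sentence ties SLUMS to it.

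**Test.** The SAP includes a between-group comparison. If the layout is group by time (an assumption, since the factors are not listed), each outcome yields three F tests: group, time, and group-by-time. The time term does not compare the groups. The plan does not say which of the other two tests the hypothesis.

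**The case against.** The strongest reply is that this is a short summary of a pilot that claims preregistration and adequate documentation. The preregistration may name ADL and mood scales. The document never says that SLUMS is the only measure, and the SAP speaks of outcomes in the plural. This stands as a limit on the conclusion, and it applies to ADL as much as to mood: what is shown is that this document states no measure, not that none was planned elsewhere or collected.

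Five stronger readings are tempting, and the text supports none of them:

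- *Mood will not be measured.* Design says that well-being will be, in both groups; what is missing is the definition.
- *There is no between-group comparison.* The SAP promises one, and Objectives give the comparator and direction; only the exact term is missing.
- *There is no baseline.* Design lists one; it is just not linked to SLUMS.
- *All three effects are confirmatory claims.* The document does not use that label and calls the study a pilot.
- *Cognition will be assessed in people other than the two groups.* Design's phrase about a similar environment can be read as describing the same participants, so nothing should rest on it.

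Pilot status does not remove the point. Objectives still state superiority on all three effects and an aim of overall effectiveness, and feasibility is not a stated aim.

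**Conclusion.** The point holds for this document. One of the three hypothesised effects (ADL) has no measure, one (mood) has an intention without a definition, and one (cognition) has a named instrument at three undated assessments. Followed as written, the plan cannot test the ADL hypothesis and supports an effectiveness conclusion on cognition only. Even that requires the SLUMS dates and the test to be stated.

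This rests on two assumptions: that the preregistration does not already name ADL and mood scales, and that SLUMS is meant as the cognitive outcome. If the first is wrong, the defect shrinks to a failure to carry the scales into this plan. The omission itself is a direct reading of the text. It should be corrected before the results are analysed, because the correction decides what the trial may conclude.

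**What to change.** Check the preregistration first. If it names ADL and mood scales, use those and copy them here. Otherwise choose one option and use the same outcome list in Objectives, Design, Methods and SAP.

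**(a) Measure all three effects.** Name one ADL scale and one mood or well-being scale, with score and rater, and give both to both groups at the SLUMS assessments. Cost: 2 scales x 3 assessments = 6 extra short administrations per participant, 9 in total with the 3 of SLUMS. If the pretest has already passed, and it was the first of the three assessments, the extra is 2 x 2 = 4. ADL and mood can then be compared between the groups at later assessments, but without adjustment for baseline and with less precision, and the report should say so. A caregiver-rated ADL scale would also add caregiver contacts. The document gives no assessment length or staffing, so the time cannot be costed.

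**(b) Narrow the claim.** Limit the effectiveness conclusion to cognition measured by SLUMS, and label ADL and mood exploratory or drop them. Cost: a text change, with two stated objectives downgraded.

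Under either option, make the first SLUMS the pretest and state when the other two occur. Name the test as the between-group difference at the last assessment, adjusted for the first. Under (a), apply it to the two added scales as well. This part needs only text, unless the first SLUMS was given after sessions began.

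### Does the Design schedule sentence put both groups with Ryan, or leave the control group's activity time dangerously open?

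*Combined protocol and SAP*

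**What the plan says.** Objectives sets up the comparison. It describes the aim as "The study will evaluate the overall effectiveness of Ryan Companionbot (aka Ryan) with interactive gameplay" and the comparator as follows: "An active control group will perform solitary physical and cognitive activities such as walking and crossword puzzles, sudoku, or solitaire". The hypothesis then sets people who play with Ryan against people who do solitary activities.

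Design states that the study "follows recommended best practices of preregistration, adequate documentation, pretest baseline, control conditions, sampling and randomization, dosing", among other items. It continues: "The pilot study will be comprised of two groups of people diagnosed with mild" dementia. The next sentence gives the only activity schedule in the document: "Subjects will play games with and administered by Ryan, 2-3 times a week and 30-minutes per day".

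Methods opens its account of the setting with "The study with Ryan CompanionBot will occur in" and names the sites. On staffing it says: "A staff member will be present during all sessions to assist with user operation, document behavioral observations, and ensure the safety of participants". Recording is by Ryan's own sensors and covers the participant's "activities and interactions including the gameplay".

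The Statistical Analysis Plan is one sentence. It names multi-way ANOVA within and between the two groups, and no time or contact variable.

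**The concern.** The schedule sentence follows directly on the mention of two groups and uses an unqualified noun. Taken at face value it could put both groups with the robot, which would remove the comparison that Objectives promises. If it covers only the Ryan group, the control group's activity has no stated frequency, length, setting or record.

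The stake is interpretation. If one group spent more time on activities than the other, a difference in cognition, daily functioning or mood could reflect time on task as well as the robot. Unequal time could inflate or hide a benefit, and minutes not noted during the study cannot be reliably recovered afterwards. Staff attendance raises a similar question, because the text does not say whether the sessions that staff attend include the control activities.

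**Working it through.** The documents state no sample size, power or expected effect, so there is no figure of the plan's own to reproduce. The check sets the passages side by side and adds simple arithmetic.

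**Inputs.** Sessions per week: 2 to 3 (Design). Minutes per session day: 30 (Design), taken as one 30-minute session on each session day. Control activity time: not stated. Study length: not stated.

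**Ryan time.** 2 × 30 = 60 minutes a week at the lower end; 3 × 30 = 90 at the upper end.

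**Reading 1: both groups play with Ryan.** This would contradict Objectives and the hypothesis. The sentence does not say that it covers everyone. The following Design sentence refers to the two groups expressly when both are meant, and Methods uses the same noun for people in dialogue with Ryan. Against that, the preceding Design sentence uses the noun for both groups, so the wording is loose. The context still decides against this reading.

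**Reading 2: the Ryan group only.** This fits Objectives, the hypothesis and the phrase about games that Ryan administers. Ryan time is 60 to 90 minutes a week and control time has no figure, so the difference cannot be computed.

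**Reading 3: one schedule for both groups.** This is an assumption, not something the text says. Let p be the share of weeks with three sessions in a group. Mean weekly time is 60(1 − p) + 90p = 60 + 30p, so Ryan minus control is 30 × (p in the Ryan group − p in the control group).

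| Case | Difference (minutes a week) | Ratio, Ryan to control |
|---|---|---|
| Same mix of 2 and 3 sessions in both groups | 0 | 1.00 |
| Ryan always 2, control always 3 | 60 − 90 = −30 | 60/90 = 0.67 |
| Ryan always 3, control always 2 | 90 − 60 = +30 | 90/60 = 1.50 |

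The outer rows need every participant in one group at one end of the range and every participant in the other group at the other end. Nothing in the documents suggests that the flexibility would be used differently by group. With no study length, no cumulative gap can be computed either.

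**Recording.** The sensors cover time with Ryan. If the staffed sessions include control sessions, an observer is there and activity time could be noted. If they do not, no record of control time is described. The text allows both.

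**Effect on the analysis.** The planned ANOVA compares the two groups on the measured outcomes. That comparison is the same whether or not minutes are logged. Minutes are also measured after allocation and form part of how each condition is delivered, so adjusting for them would not by itself isolate the robot's effect.

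**The case for a change.** The strongest case for a change accepts Reading 2 and argues that it makes matters worse, because the control group's activity time is then wholly unspecified. Design claims good practice on control conditions and dosing but gives no control schedule. The aim is effectiveness with significance testing, so calling the study a pilot does not excuse the gap. The remedy looks cheap: a few lines of text and a simple log.

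Much of the factual part stands. A reader cannot tell from the document how long or how often the control group is active, or who observes it. Equal time is not assured.

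The step from there to a required change does not stand. Neither the objective nor the hypothesis promises a comparison at equal time, and the good-practice sentence does not promise matching. Ryan sessions against solitary activity, each as delivered, is a legitimate contrast for a pilot, and staff help can fairly be seen as part of delivering Ryan. Writing down the control arrangements would record what the team must settle anyway to run the group.

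The log would be a reporting addition. Where staff are absent it would depend on a diary kept by or for people with dementia, set beside attended and sensor-recorded sessions in the other group. The two sets of minutes would then differ in accuracy, which weakens their use for explaining a group difference.

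**Conclusion.** No change follows. The apparent contradiction is loose wording that Objectives resolves. The unstated control schedule, setting and staffing are a gap that the study team fills sensibly in practice. No rule in the plan has been shown to give a wrong answer, and the proposed log would alter no planned analysis.

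No size or direction of bias can be given. The ±30 minutes a week is an extreme bound on an assumed common schedule, not an expected difference.

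This rests on two assumptions: that the schedule sentence describes the Ryan group, as the hypothesis implies, and that the result is read as Ryan sessions against solitary activity as each was delivered. A claim about the robot's effect at equal activity time would go beyond what the documents set out to show.

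### The SAP seeks significance within as well as between groups and does not say that only the Ryan-minus-control difference in change tests the comparative hypothesis

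*Combined protocol and SAP*

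**What the plan says.** **Objectives.** The aim is to evaluate Ryan's overall effectiveness in terms of a positive impact on the user. The hypothesis that follows is comparative: people playing with Ryan "will have a greater positive effect on cognitive function, performance of activities of daily living, and mood compared to individuals engaging in solitary" activities. The comparator is named: "An active control group will perform solitary physical and cognitive activities such as walking and crossword puzzles, sudoku, or solitaire".

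**Design.** The best practices that the study says it follows include a pretest baseline and "control conditions, sampling and randomization, dosing, blinding, contingent analysis". On what will be measured, the section says: "The team will measure the changes and improvement in the social/emotional well-being of these two groups and eventual changes in the cognitive/memory functions". It names no contrast between the groups.

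**Methods.** SLUMS is scored from 0 to 30, and "The measurement will be conducted three times throughout the study". Timing and alternate test forms are not mentioned.

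**Statistical Analysis Plan.** The whole plan is one sentence. It begins "Statistical analysis will include multi-way Analysis of Variance (ANOVA) to find the significance of the findings" and goes on to "the effect of different parameters and variables on the measured outcomes within and between the two groups". It names no group-by-time interaction or difference in change, does not call within-group results descriptive, and does not say which result would support a conclusion of effectiveness.

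**The concern.** A claim that one condition does better than another can be tested only by comparing the two. Change within one arm has no comparator. In this study at least two forces other than Ryan can move a score over time. One is familiarity with a test given three times. The other is the course of the dementia. They push in opposite directions, and the documents do not allow their net effect to be predicted.

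Two errors become possible if within-arm significance is available as a result:

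- **Shared gain.** If retest learning dominates, the Ryan arm can improve significantly when Ryan is no better than solitary activity. The pattern of a significant result with Ryan and a non-significant one in control is easily read as a difference, although no difference has been tested.
- **Shared decline.** If disease course dominates, a real slowing by Ryan shows up in its own arm as no improvement, or even as worsening. Framing the target as improvement invites reading that as failure.

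This is separate from multiplicity and from how repeated measurements enter the model. A single, correctly executed within-arm test would still not answer the stated question.

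**Working it through.** **Step 1: match each statement to the contrast it implies.**

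| Place | Statement | Contrast |
|---|---|---|
| Objectives, hypothesis | Greater effect than solitary activity | Between groups |
| Design | Changes and improvement in the two groups | None named |
| SAP | Significance and effects within and between groups | Both, with neither tied to the hypothesis |

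Write the expected change as S + R in the Ryan arm and S in control. S is the shared shift from retest learning and disease course, and R is the effect of the Ryan condition relative to solitary activity. A within-arm test in the Ryan arm tests S + R = 0. The between-group difference is (S + R) − S = R. Only the second is the hypothesis. S cancels in expectation if allocation is random and both arms follow the same testing schedule.

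**Step 2: how far a within-arm test could mislead.** The documents state no sample size, alpha, SD or effect size, so there is no figure to reproduce. Every input below is assumed, for illustration only:

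- R = 0 and S = +0.5 or +1 SLUMS point
- SD of change 3 points
- n = 10, 20 or 30 per arm, arms independent
- paired t-test in each arm, two-sided 5%

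Formulas: noncentrality = (S/3) × √n with n − 1 degrees of freedom. P(up) is the probability that the noncentral t exceeds the upper 2.5% critical value. P(pattern) = P(up) in the Ryan arm × P(not significant) in control.

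Example, S = 1 and n = 20: noncentrality = (1/3) × √20 = 1.491; critical value 2.093 on 19 degrees of freedom; P(up) = 0.2932; P(not significant) = 0.7065; P(pattern) = 0.2932 × 0.7065 = 0.207.

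| Shared gain | n per arm | Significant improvement in Ryan arm | Ryan significant, control not |
|---|---|---|---|
| 1 point | 10 | 16% | 13% |
| 1 point | 20 | 29% | 21% |
| 1 point | 30 | 42% | 24% |
| 0.5 point | 10 | 7% | 6% |
| 0.5 point | 20 | 11% | 9% |
| 0.5 point | 30 | 14% | 12% |

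The reference for the third column is the nominal 2.5% for improvement. Under the same assumptions, a between-group test of change falsely favours Ryan in 2.5% of trials.

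**Step 3: the opposite direction.** The t-test is symmetric, so the 1-point rows can be mirrored. Suppose the Ryan arm loses 1 point and control loses more, so that Ryan helps. The within-arm test then finds significant *worsening* with Ryan in 16%, 29% and 42% of trials (n = 10, 20, 30), and significant improvement in under 1%. A true benefit would be reported as none. Shared decline also means that false claims of improvement become rare, so the table in Step 2 applies only if the net shared shift is a gain.

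**The case against.** **The plan never says that within-group change counts as proof.** A reader might infer that it does, or that within- and between-group results have equal standing. The documents do not support that. The hypothesis is explicitly comparative, an active control is named, baseline and randomization are listed, and the SAP sentence covers the between-group comparison too. The Design sentence only says that change will be measured in both groups, which any comparison needs. This stands. The defect is that the plan leaves the within-arm route open and does not name the test of the hypothesis.

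**The SAP wording may describe a mixed ANOVA**, with time as the within factor and group as the between factor. Its interaction would be the right kind of contrast. That is a fair reading of a design with three measurements. But the text says multi-way, refers to effects within the groups, and names no interaction, so the reading has to be written down before it can be relied on.

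**Other tempting arguments go too far.** Regression to the mean would need selection on a low score. The documents give SLUMS bands but no entry cut-off. Nor does the novelty of the robot cancel between arms: it belongs to the Ryan condition only, so the between-group difference includes it. The point here needs only retest learning and disease course.

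**The figures are not estimates for this trial.** This also stands. Gain, SD and sample size are all assumed.

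**Conclusion.** The concern holds in a limited form. The SAP seeks significance within and between groups without reserving the test of a comparative hypothesis for the between-group difference in change, and Design frames the target as improvement. Within-arm tests carried out as the text allows could produce a misleading statement about effectiveness in either direction. That goes beyond missing detail, but it falls short of a plan that has adopted within-arm change as its evidence.

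The size in this trial is unknown. On the assumed inputs (shared gain 0.5 to 1 point, SD of change 3, 10 to 30 per arm, no Ryan effect), significant improvement appears in the Ryan arm in 7% to 42% of trials, and the misleading split between arms in 6% to 24%. The conclusion does not depend on those figures. It rests on the algebra in Step 1, and on retest learning and disease course being plausible in people with dementia who are tested three times. The change should be made: the control arm already exists and the right analysis needs no further data.

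**What to change.** **SAP.** State that the hypothesis is tested only by the Ryan-minus-control difference in change from baseline, as a group-by-time interaction or by ANCOVA adjusted for the baseline score. Keep time as a within-person factor where all three measurements are used. Simply deleting the reference to within-group effects would not do, because it could be read as removing the time factor. Name the outcome and time point to which the contrast applies: with two groups and three measurements the interaction has (2 − 1) × (3 − 1) = 2 degrees of freedom and does not by itself show a direction in Ryan's favour. Report within-group changes with confidence intervals, as descriptive only.

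**Design.** Replace improvement in the two groups with the difference between the two groups in change from baseline, so that slower decline counts as benefit.

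**Cost.** A few sentences of wording and no new data. The sponsor gives up within-group p-values as evidence of effectiveness.

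### Does the plan need randomisation within facility and a facility term in the ANOVA because sessions run at two facilities?

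*Combined protocol and SAP*

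**What the plan says.** Three places in the combined protocol and SAP bear on this.

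- **Methods** gives the setting: "The study with Ryan CompanionBot will occur in ESC's and Kavod's library or atrium or a location free of distractions and intrusion". I read the two names as two separate facilities, which is an inference from the wording. The number of participants at each is not given.
- **Design** lists, among practices the study follows, "control conditions, sampling and randomization, dosing, blinding, contingent analysis, statistical analysis". No allocation method, ratio, blocks or strata are given. The same section says "The team will measure the changes and improvement in the social/emotional well-being of these two groups", and it describes the participants' surroundings as alike.
- **Statistical Analysis Plan** is one sentence. It opens "Statistical analysis will include multi-way Analysis of Variance (ANOVA) to find the significance of the findings" and goes on to "the effect of different parameters and variables on the measured outcomes within and between the two groups". No factor is listed, so facility is neither named nor ruled out.

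The documents state no sample size, alpha, power, target difference, SD or facility difference.

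**The concern.** With two facilities, a statistician expects the allocation to be balanced within each and the analysis to carry a facility term. Without the first, the arms can by chance draw unequally from the two facilities. Without the second, any difference between facilities stays in the residual error.

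In a small pilot such imbalance is common. With equal facilities and equal arms, the arms' facility shares differ by 20 percentage points or more in 66%, 47% and 34% of random allocations at a total of 20, 30 and 40 participants. Both measures look nearly free: a second randomisation list and one degree of freedom. What would be at stake is precision on cognitive function, activities of daily living and mood.

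**Working it through.** **Inputs.** The plan has no figure to reproduce. The documents supply two facilities, two groups and a multi-way ANOVA. Everything else is assumed: total N from 10 to 40, 1:1 allocation, equal facilities, within-facility SD of 1, two-sided alpha of 0.05, and a facility gap g of 0 to 0.8 SD on the analysed outcome.

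**Step 1: chance imbalance.** Let n = N/2 be the arm size, and let K be the number in one arm from the first facility, which is hypergeometric. The facility shares differ by |2K/n − 1|. The probability that this is at least 0.2 is 0.656, 0.466 and 0.343 at N = 20, 30 and 40.

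**Step 2: validity.** Imbalance of this kind is part of the randomisation distribution. Simulated type I error of the unstratified, unadjusted test is 0.049 to 0.051. The comparison is neither biased nor anticonservative.

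**Step 3: precision.** The ratio of 95% CI width without both measures to width with both is approximately

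t(N−2)/t(N−3) × √(1 + s(1−s)g²·N/(N−1)),

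where s is one facility's share of participants and t(ν) is the 97.5% point on ν degrees of freedom. A ratio above 1 favours the measures. For N = 20, s = 0.5, g = 0.3:

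- t(18)/t(17) = 2.101/2.110 = 0.996
- √(1 + 0.25 × 0.09 × 20/19) = √1.0237 = 1.012
- product = 1.008

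The table gives simulated ratios, except the g = 0 entries for N = 20 to 40, which come from the formula. With 15 per facility, exact 1:1 within facility is impossible. Splits of 8:7 and 7:8 carry information 2 × (8×7/15) = 7.467 against N/4 = 7.5, so the formula is multiplied by √0.9956.

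| Total N | g = 0 | g = 0.3 | g = 0.5 | g = 0.8 |
|---|---|---|---|---|
| 10 (5 per facility, 3:2 and 2:3) | 0.959 | 0.973 | 0.994 | 1.044 |
| 12 (6 per facility) | 0.988 | 1.000 | 1.021 | 1.072 |
| 20 | 0.996 | 1.008 | 1.029 | 1.077 |
| 30 (15 per facility) | 0.996 | 1.008 | 1.027 | 1.076 |
| 40 | 0.999 | 1.011 | 1.031 | 1.078 |

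With a 70:30 facility split and N = 20 to 40, the gains are 0.6–0.9%, 2.2–2.6% and 6.3–6.6% at g = 0.3, 0.5 and 0.8.

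In participants, N × (ratio² − 1) gives 0.3, 1.2 and 3.2 at N = 20, and 0.9, 2.5 and 6.5 at N = 40.

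**Step 4: break-even.** Setting the ratio to 1 gives g of about 0.18 SD at N = 20, 0.17 at N = 30 with 15 per facility, and 0.08 at N = 40. At N = 12 it is about 0.3, and at N = 10 with 5 per facility about 0.56 to 0.59. Below these gaps the measures widen the interval.

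**Step 5: which gap matters.** If change from baseline is analysed, g is the facility gap in *change*, in units of the SD of change, because a stable difference in level cancels within each participant. In a group-by-time test over the three SLUMS measurements, a facility main effect likewise gains essentially nothing; only a facility-by-time difference would matter. A gap of 0.5 to 0.8 SD in change is a far stronger assumption than the same gap in level.

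**Step 6: each measure alone.** Stratifying without the term makes the test conservative: type I error is 4.8%, 4.3–4.4% and 3.5–3.7% at g = 0.3, 0.5 and 0.8. The term without stratification is valid. At N = 20, 30 and 40 it widens the interval by about 2.1%, 0.8% and 0.3% at g = 0.3, and narrows it by about 4.6%, 5.8% and 6.4% at g = 0.8. So analysts who later add facility to the ANOVA lose no validity, and can lose or gain a little width.

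**The case for a change.** The best case for a change is that it costs almost nothing and fits what is planned. A multi-way ANOVA is already intended, so facility would be one more named factor, and naming it in advance prevents it being added or dropped after the results are seen. From N = 20 upwards the direction is favourable unless the gap is small, and at 0.8 SD the gain reaches about 8% of interval width. This stands as an argument for a reasonable option. It does not show that the plan goes wrong without it. The documents give no sign that the facilities differ, and their remark on similar surroundings points to the low end of the range.

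A more serious version is that the text never says both arms are formed within each facility. If arms had followed facility and facility explained 5% of outcome variance, a false difference would be declared with probability about 0.16 at N = 20 and 0.29 at N = 40. But the documents do not say this was done, and Design claims randomisation. A facility term could not repair such a design, because group and facility would be inseparable. That is a question about the allocation method as a whole, which the document leaves unstated.

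**Conclusion.** No change follows. The omission is real, but it is missing detail with no demonstrated harm. Under individual randomisation the comparison is unbiased and keeps its 5% type I error. The forgone precision is about 1% of CI width at an assumed 0.3 SD facility gap and about 3% at 0.5 SD, for 20 to 40 participants at equal facilities. It is nil or slightly negative if the facilities do not differ, or in a pilot of about 10 to 12 with a small gap. Even the sign depends on a sample size and a facility gap in the analysed outcome that the documents do not give. Because the plan points to change, a stable gap in level would not count.

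The sponsor may still choose to randomise within facility. If so, the analysis should include facility, with facility by time if repeated measurements are analysed together, to avoid a conservative test. The unspecified ANOVA permits that as it stands. The unstated sample size, allocation method and model factors matter more than this refinement.
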